The study population will include adults who were fully vaccinated against SARS-CoV-2 virus (i.e., two doses of Pfizer or Moderna vaccines or one dose of the J&J vaccine), and have received a Roche SARS-CoV-2 Semi-Quant Spike Ig Ab test at least 3 weeks after full vaccination as part of their usual clinical care at AHF Midtown Manhattan Healthcare Center.

Incidence rates of COVID vaccine response levels (i.e., adequate, low, non-response) will be estimated using univariate Poisson regression, overall and by vaccine type. Among individuals with at least two antibody measurements, rates of antibody levels decay will be estimated using univariate linear regression, overall and stratified by HIV status, vaccine type and baseline CD4 cell count. In the sub-population of individuals who received a COVID vaccine booster, vaccination and antibody response will be characterized at least 3 weeks after the booster is received. Univariate linear regression will be used to estimate rates of antibody levels decay, among individuals with at least two antibody measurements, including one after the booster dose. Rates of response decay will be produced overall, and stratified by HIV status, booster type and baseline CD4 cell count.

2. Introduction

BACKGROUND

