Limited real-world data are available on the antibody response after COVID-19 vaccination comparing HIV-negative and HIV-positive individuals. There are also limited information that would allow the potential usage of quantitative antibody testing to determine those at greatest risk for infection while could help in guiding the timing of additional vaccinations. There are also limited information on the antibody response of vaccine boosting in individuals, especially those with altered immune response that might lead to no response or low response to the primary vaccination series. At the moment, clinicians must rely on clinical judgement when advising their patients on the utility of vaccine boosting, as well as their level of protection from COVID vaccination. Additional information would be helpful in informing decisions on third doses in different populations such as HIV positive people, whose responses to COVID-19 vaccine and immune status would help define the timing and need for an additional vaccination based on current recommendations. Real-world evidence is needed to better inform such decisions.

3. Research Objectives

PRIMARY OBJECTIVE(S)

Objective #1: Describe COVID-19 vaccine response including frequency of non-response, low response, and adequate response as measured by antibody test by HIV status (e.g., rates, and relationship to demographic and clinical characteristics, as well as vaccine types)

Objective #2: Describe rate of decline in antibody levels over time by HIV status, vaccine type, and baseline CD4 count after initial vaccination as well as other parameters.

SECONDARY OBJECTIVE(S)

Objective #3: Describe response to COVID-19 boosters given (vaccine types, concordant vs. discordant boosters, duration from initial vaccine completion, antibody response, and side effects)

Objective #4: Describe rate of decline in antibody levels over time by HIV status, baseline CD4 count, by vaccine given, and after booster vaccination

Objective #5: Recording breakthrough infections after vaccinations and assessing antibody levels pre-breakthrough infection

4. Data Source

AHF MIDTOWN MANHATTAN HEALTHCARE CENTER

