The AHF Midtown Manhattan Healthcare Center is part of the AIDS Healthcare Foundation (AHF) network. AHF is a global nonprofit organization providing cutting-edge medicine and advocacy to over 1,500,000 people in 45 countries. Currently, the AHF Midtown Manhattan Healthcare Center provides care for 993 HIV-positive and 946 HIV-negative individuals who have had at least one clinical contact in the past 24 months.

Among HIV-positive patients active in care at AHF Midtown Manhattan Healthcare Center, the median age is 53 years (IQR: 38, 61); 95% are men, 22% are Black and 19% are Hispanic. Most HIV-positive patients have their healthcare covered by commercial insurance (52%), Medicaid (29%), Medicare (16%) and/or ADAP/Ryan White (14%). The median follow-up time at AHF Midtown Manhattan Healthcare Center is 7.3 years (IQR: 2.3, 8.6); 14% have at least 10 years of follow-up.

Among HIV-negative patients active in care at AHF Midtown Manhattan Healthcare Center, the median age is 44 years (34, 56); 91% are men, 11% are Black and 16% are Hispanic. Most have their healthcare covered by commercial insurance (70%) or Medicaid (18%). The median follow-up time at AHF Midtown Manhattan Healthcare Center is 4.9 years (IQR: 1.6, 7.9); 8% have at least 10 years of follow-up.

DESCRIPTION OF THE DATABASE AND PREPARATION OF ANALYTICAL FILES

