To normalize across different neutralization assays utilized in phase 3 studies of various COVID-19 vaccines, Khoury, et al., estimated that a 50% protective neutralization level equivalent to 20% of the mean titer in the convalescent subjects equates to a measured in vitro neutralization titer of between 1:10 and 1:30 was approximated at 54 international units IU/ml (95% CI 30–96 IU/ml) against wild-type CoV-19 infection.^{xx} During the period of COVID-19 infection where the Delta virus predominated, a quantitative spike Ab's >250 IU/mL was deemed adequate, based on studies that show that an antibody titer of 4-6x wild-type SARS-CoV-2 were required to effectively neutralize Delta viral strains.^{xxi,xxii, xxiii} We thus utilized a threshold level of >250 (5x wild-type ab levels) IU/mL as an adequate vaccine response against circulating Delta virus post last vaccination recommended in a series, a level of <50 IU/mL as a non-responsive post vaccination titer (inadequate for even wild-type Co-V-2 infection), and levels between (50-250 IU/mL) as a low vaccine response. Non and low-responders who had Co-V-2 Spike Ig levels that were inadequate based on the correlation of Spike Ig levels and neutralizing ab correlations relative to the predominant circulating viral strains were offered optional booster vaccinations with subsequent antibody response measurement post vaccination as standard of care. These recommendations are the current one's implemented during the Delta Co-V-2 19 outbreak by the Ministry of Solidarity and Health of France and the COVID Guidelines group in Geneva, where 260 IU/mL and 300 IU/mL, respectively, are considered gray zones of antibody protection against the Delta virus and where booster vaccinations are recommended for consideration.^{xxiv, xxv}

STUDY COVARIATES

Covariates of interest include: age, sex, race, ethnicity, HIV status, region, payer, immunosuppressive conditions, CD4 cell count, comorbid conditions, BMI. This information will be obtained from each patient's electronic health records.

7. Statistical Analysis

ANALYSIS OF DEMOGRAPHICS/BASELINE CHARACTERISTICS

Demographic and clinical characteristics will be summarized in the overall population using medians with interquartile ranges (IQR) for continuous variables and frequencies with proportions for categorical variables.

ANALYSIS OF PRIMARY OBJECTIVES

Objective #1: COVID-19 vaccine non-response and low response as measured by antibody test by HIV status

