Records will be examined retrospectively to determine which patients, both HIV-positive and negative, were non-responders, or who developed low or adequate quantitative Ig spike antibodies using the Roche Elecsys semi-quantitative spike Ab Ig assay during usual clinical care.

Demographic and clinical characteristics will be summarized by vaccine response level using medians with interquartile ranges (IQR) for continuous variables and frequencies with proportions for categorical variables. Statistical comparisons between vaccine response level will be performed using Pearson's chi-square or Fisher exact tests for categorical variables and Wilcoxon rank-sum test for continuous variables, using an adequate response as the comparator.

Incidence rates and 95% confidence intervals of COVID vaccine adequate response, non-response and low response to COVID vaccines will be estimated using univariate Poisson regression. Incidence rates will be obtained both overall and by vaccine type. The incidence rate is defined as the number of events during follow-up divided by person-time at risk of the event. Estimating incidence rates with Poisson regression allows the use of all person-time time at risk of the outcome, even with differential lengths of follow-up between groups.

Objective #2: Rate of decline in antibody levels over time by HIV status, vaccine type, and baseline CD4 count after initial vaccination

Rates and 95% confidence intervals of antibody levels decay will be estimated among individuals with at least two antibody measurements. Univariate linear regression, will be employed, using the continuous antibody level as the dependent variable, and timing of tests as

the dependent variable. Robust variance estimator will be used to account for repeated measures. Rates of decay will be produced overall, and stratified by HIV status, vaccine type and baseline CD4 cell count.

ANALYSIS OF SECONDARY OBJECTIVES

Objective #3: COVID-19 boosters given

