In the sub-population of Individuals who received a COVID vaccine booster, the following characteristics will be described using medians with interquartile ranges (IQR) for continuous variables and frequencies with proportions for categorical variables: initial and booster vaccine types, concordant vs. discordant boosters, duration between initial vaccine completion and booster dose, antibody response after the booster, and side effects recorded. Post vaccination responses will be determined no earlier than 2 weeks post vaccination.

Objective #4: Rate of decline in antibody levels over time by HIV status, booster type, and baseline CD4 count after booster vaccination

Rates and 95% confidence intervals for changes in antibody levels will be estimated using linear regression, among individuals with at least two antibody measurements, including one after the booster dose. Univariate linear regression, will be employed, using the continuous antibody level as the dependent variable, and timing of tests as the dependent variable. Robust variance estimator will be used to account for repeated measures. Rates of decay will be produced overall, and stratified by HIV status, booster type and baseline CD4 cell count.

Objective #5: Recording breakthrough infections after vaccinations and assessing antibody levels pre-breakthrough infection

Among all individuals with full vaccination and antibody testing, the EHR will be searched for documentation of COVID infection after vaccinations. If breakthrough infections are observed, antibody levels prior to infection will be described. Note: COVID infections may not be recorded in the EHR if diagnosed outside of the clinic.

SENSITIVITY ANALYSES

NA

SUBGROUP ANALYSES

Patients provided COVID boosters will be evaluated by the types and combinations of vaccines they received. Further, patients given sequential antibody tests will be evaluated by vaccine type for response over time.

8. Study Conduct

REGULATORY AND ETHICAL CONSIDERATIONS

OPERA® complies with all HIPAA and HITECH requirements and has received annual institutional review board (IRB) approval by Advarra IRB, including a waiver of informed consent and authorization for use of protected health information

INFORMED CONSENT

Informed consent has been waived for this non-interventional, observational research and authorization for use of the protected health information has been approved by Advarra IRB.

DATA PRIVACY & PERSONALLY IDENTIFIABLE INFORMATION (PII)

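### Decay by baseline CD4 count (Objectives #2 and #4) is planned only through unspecified strata, so the CD4 gradient is estimated inefficiently and depends on the split chosen

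*Combined protocol and SAP*

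**What the plan says.** Section 3 makes CD4 part of a primary objective, Objective #2: "Describe rate of decline in antibody levels over time by HIV status, vaccine type, and baseline CD4 count". Objective #4 repeats the aim after booster vaccination.

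Section 7 gives the method. For Objective #2: "Rates of decay will be produced overall, and stratified by HIV status, vaccine type and baseline CD4 cell count". For Objective #4: "Rates of decay will be produced overall, and stratified by HIV status, booster type and baseline CD4 cell count". The Synopsis describes the initial-series analysis in the same terms: "overall and stratified by HIV status, vaccine type and baseline CD4 cell count".

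The model under both objectives is "Univariate linear regression, will be employed, using the continuous antibody level as the dependent variable, and timing of tests as the dependent variable". The second "dependent" is evidently a slip for the explanatory variable. Either way, test timing is the only regressor.

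Section 6 lists CD4 for the cohort as a whole: "Covariates of interest include: age, sex, race, ethnicity, HIV status, region, payer, immunosuppressive conditions, CD4 cell count, comorbid conditions, BMI". The document does not state cut-points, a number of strata, a time window for baseline CD4, whether the CD4 strata are confined to HIV-positive patients, or what happens when no CD4 count is on file. Sensitivity analyses are entered as not applicable.

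**The concern.** CD4 count is continuous. Dividing it into strata and fitting a separate line in each treats everyone within a stratum as alike, and leaves the reader to infer a gradient by comparing a few slopes. With no cut-points in the document, nothing in it prevents the split from being settled after the retrospective records have been examined, and no sensitivity analysis would show whether the answer changes with the split.

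This bears on the study's purpose. The Rationale in Section 2 says that vaccine response and immune status in HIV-positive people would help define when another vaccination is needed. CD4 is the plan's continuous measure of that immune status, so an imprecise or split-dependent CD4 result weakens a named part of a primary objective.

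**Working it through.** The plan states no sample size, power, CD4 distribution or stratum size, so it has no figure to reproduce. The check asks how much information on a linear CD4 gradient survives stratification, and what can be said about stratum size.

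**1. Information kept**

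Assumptions, not from the documents: CD4 is normal and its effect on the decay slope is linear. The share of information kept is the between-stratum variance of CD4 divided by its total variance:

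E = Σ [φ(z_lower) − φ(z_upper)]² / p

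The sum runs over strata, φ is the standard normal density, and p is the share of patients in the stratum.

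- Median split: 2 × 0.3989² / 0.5 = 0.637, a loss of 36%.
- Tertiles: 2 × 0.3636² / 0.3333 + 0 = 0.793, a loss of 21%.
- Quartiles: 2 × 0.3178² / 0.25 + 2 × (0.3989 − 0.3178)² / 0.25 = 0.808 + 0.053 = 0.861, a loss of 14%.
- Lowest 10% against the rest: 0.342, a loss of 66%.
- Lowest 5% against the rest: 0.224, a loss of 78%.

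For cuts at 200 and 500, a mean and SD must also be assumed:

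| Assumed mean / SD | z at 200, 500 | Shares below 200, 200-499, 500 and above | E | Loss |
|---|---|---|---|---|
| 550 / 250 | −1.40, −0.20 | 8.1%, 34.0%, 57.9% | 0.278 + 0.171 + 0.264 = 0.713 | 29% |
| 650 / 280 | −1.61, −0.54 | 5.4%, 24.2%, 70.4% | 0.223 + 0.230 + 0.170 = 0.622 | 38% |
| 750 / 300 | −1.83, −0.83 | 3.3%, 16.9%, 79.8% | 0.166 + 0.255 + 0.100 = 0.520 | 48% |

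**2. Size of a low-CD4 stratum**

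The only count available is that the clinic "provides care for 993 HIV-positive and 946 HIV-negative individuals who have had at least one clinical contact in the past 24 months". The 993 are a ceiling. They have not yet been reduced by vaccination, antibody testing (done for only some patients), the need for two measurements, or, for Objective #4, a booster. Count = 993 × assumed share in the decay set × assumed low-CD4 share:

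| Share of the 993 in the decay set | 5% low CD4 | 10% | 20% |
|---|---|---|---|
| 10% (99 patients) | 5 | 10 | 20 |
| 20% (199) | 10 | 20 | 40 |
| 40% (397) | 20 | 40 | 79 |
| 100% (993) | 50 | 99 | 199 |

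The count runs from 5 to 199 depending on inputs that the documents do not supply.

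**3. Can CD4 enter in any other way?**

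Not in the decay analyses: a univariate regression on test time has no place for a CD4 term or a CD4-by-time term. Under Objective #1, continuous characteristics are compared across response levels by "Wilcoxon rank-sum test for continuous variables, using an adequate response as the comparator", which needs no cut-points. The gap is therefore specific to decay.

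**The case against.** The objectives are descriptive. No CD4 trend test or power target is stated, and E measures efficiency for a linear trend. Section 9 says that analysis specifications contain definitions of key variables and of baseline, so cut-points may be fixed elsewhere. On this view the plan needs only a line stating the cut-points, the baseline window and the population.

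Part of this stands. The consequence is imprecise description, not a failed powered test, and it is fair to say only that cut-points are not stated in this document. But an estimate that is imprecise or moves with the split is also poor description. Section 9 is generic and supplies no CD4 definition for this study.

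Four stronger readings are tempting and are not supported:

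- **That the low-CD4 stratum will be tiny.** The documents name no such stratum and give no CD4 distribution or number with two tests. It may be small.
- **That much of the CD4 information is necessarily lost, as if those patients had not been analysed.** The loss could be as low as 14%, and it concerns only the CD4 gradient. Every eligible patient still contributes to the overall and HIV-status decay rates.
- **That CD4 results cannot be set against HIV-negative patients.** Stratifying by HIV status yields an HIV-negative rate with a 95% CI, which can be placed beside each CD4 stratum. A continuous model would only locate a departure more finely.
- **That the plan treats CD4 as relevant only in HIV.** It lists CD4 for the whole cohort and does not say to whom the CD4 strata apply.

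A last objection is that a continuous model does not create data at low CD4. With three knots at the 10th, 50th and 90th percentiles, a restricted cubic spline is linear below the 10th percentile. Under the assumed distributions that is a CD4 count of about 230, 291 or 366. An estimate at 200 would rest on the same few patients plus shape borrowed from higher counts. This is correct, and it limits which CD4 values should be reported.

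**Conclusion.** The point holds as an inexpensive improvement to a named part of a primary objective and its secondary counterpart. As written, the plan estimates the CD4 gradient inefficiently and lets it depend on an unstated split. The size depends on that split: 14% of the gradient information for quartiles, 36% for a median split, 29-48% for cuts at 200 and 500, and up to 78% if the lowest 5% are set against the rest. These figures rest on a normal CD4 distribution and a linear effect, and the 200/500 range also on the assumed means and SDs. None of these inputs comes from the documents.

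**What to change.** Add to Section 7, for Objectives #2 and #4:

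- Among HIV-positive patients, fit a model with continuous CD4 (linear or restricted cubic spline), time and a CD4-by-time term, keeping the planned robust variance.
- Define baseline CD4 as the last value before the first dose for Objective #2, and the last value before the booster for Objective #4. State how patients without such a value are handled.
- For Objective #4, use post-booster measurements only. The current rule asks for two measurements of which one follows the booster, so a slope could otherwise include the rise produced by the booster and would not be decay.
- Report decay rates with 95% CIs at CD4 values fixed in advance within the well-supported range, beside the HIV-negative rate.
- Keep a descriptive table by CD4 strata, with cut-points fixed in advance and the number of patients and tests in each.

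The cost is analysis wording and one extra model on data already in the health records. The downside is an assumed smooth CD4 shape: low-CD4 estimates are partly borrowed from higher values and should be flagged as such. Dropping pre-booster measurements may also reduce the data for Objective #4, by an amount the documents do not allow one to estimate.

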“Should COVID-19 Quantitative Antibody Titers be Implemented to Guide COVID-19 Booster Vaccinations Regardless of HIV status, Immunosuppression, or Age?”

**Study Protocol
Version 2.5**

.....

Prepared by:

[name], [name], and [name]

October 29, 2021

Table of Contents

Contents

1. SYNOPSIS	3
2. INTRODUCTION	4
BACKGROUND	4
RATIONALE FOR THE STUDY	6
3. RESEARCH OBJECTIVES	7
PRIMARY OBJECTIVE(S)	7
SECONDARY OBJECTIVE(S)	7
4. DATA SOURCE	8
AHF MIDTOWN MANHATTAN HEALTHCARE CENTER	8
DESCRIPTION OF THE DATABASE AND PREPARATION OF ANALYTICAL FILES	8
5. STUDY POPULATION	11
INCLUSION CRITERIA	11
EXCLUSION CRITERIA	11
6. STUDY DESIGN	12
OVERVIEW OF STUDY DESIGN	12
EXPOSURES OF INTEREST	12
SUBGROUPS OF INTEREST	12
STUDY ENDPOINTS	12
STUDY COVARIATES	13
7. STATISTICAL ANALYSIS	14
ANALYSIS OF DEMOGRAPHICS/BASELINE CHARACTERISTICS	14
ANALYSIS OF PRIMARY OBJECTIVES	14
ANALYSIS OF SECONDARY OBJECTIVES	15
SENSITIVITY ANALYSES	15
SUBGROUP ANALYSES	16
8. STUDY CONDUCT	17
REGULATORY AND ETHICAL CONSIDERATIONS	17
INFORMED CONSENT	17
DATA PRIVACY & PERSONALLY IDENTIFIABLE INFORMATION (PII)	17
ADVERSE EVENT REPORTING	17
9. ADMINISTRATIVE MATTERS	18
QUALITY ASSURANCE	18
10. REFERENCES	19

1. Synopsis

Little real-world data are available on the antibody response after COVID-19 vaccination in HIV-negative and HIV-positive individuals, the potential usage of quantitative antibody testing to determine those at greatest risk for infection while helping guide additional vaccination timing, and the antibody response of vaccine boosting in individuals with no response or low response to initial vaccinations. At the moment, clinicians must rely on general category recommendations and clinical judgement when advising their patients on the utility of vaccine boosting, as well as their level of protection from COVID vaccination. Real-world evidence is needed to better inform such decisions. The aim of this study is to assess levels of COVID-19 vaccine response through measuring surrogate Ig spike antibody measurements, to determine the rates of antibody level decay after vaccination, and to measure the efficacy of utilizing these antibody measurements to help guide the timing of booster doses among HIV-negative and HIV-positive patients.

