Currently, there is little guidance as to when to give a COVID-19 booster vaccine, particularly for those under the age of 65, the non-immunosuppressed, and with those with different types of immune modifying conditions. Clinicians have thus been asked to use clinical judgement and patient discussion to determine if such a booster vaccine is appropriate, leading to great variability in practices. In addition, there is limited real-world evidence of vaccination response both amongst vaccination type and amongst differing patient populations. Hence, individuals who have been vaccinated, may assume they are protected, but in actuality have not developed, or sustained a protective antibody response. Conversely, some people may fall into a category for which vaccinations may be given, but there are limited data to support giving an additional dose of vaccine, especially if they lie outside the guidance established for the age over 65 and immunosuppressed patient populations. However, the potential need to proactively give additional vaccinations in this population are exemplified in studies in Israeli healthcare workers as well as in the general population which show that post vaccination waning antibody levels are highly correlated with risk of re-infection, severe disease, and hospitalization and booster vaccination is correlated with decreased incidence rates.^{i,ii} In contrast, those patients with sufficient antibody titers, who otherwise would have received an additional vaccine through general age and timeline guided recommendations, would no longer need to receive the additional vaccination, thus potentially conserving resources for those in greatest need such as for countries deficient in primary vaccinations. Although the totality of an individual's immune response from a primary vaccine series may mostly control severe COVID-19 illness leading to hospitalizations, in states where there are inadequate primary vaccination rates, even mildly symptomatic vaccinated carriers of the virus may serve as sources for the continued propagation of SARS-CoV-2 infection and further inhibition of pandemic control. Super-spreader congregations of even mostly vaccinated populations, like in the outbreak reported by the MMWR in Massachusetts, further exemplify the continued propagation of the virus to both vaccinated and unvaccinated individuals.ⁱⁱⁱ

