Additional vaccine doses may be particularly important for healthcare providers who are often in direct contact or close proximity to SARS-CoV-2 infected individuals, where resurgences of SARS-CoV-2 infection have been reported across the U.S., especially in the era of the SARS-CoV-2 Delta strain.^{iv,v} In addition, the odds of long COVID-19 symptomology were estimated in one study to be 50% less in the vaccinated versus the insufficiently immunized population.^{vi} In contrast, those healthcare workers who have sufficient immunogenicity against prevalent SARS-CoV-2 strains, may not fit the compartmentalization into time-based vaccination strategies, but rather individualized immunologic responses to vaccinations. Furthermore, due to the

interpersonal variability of immunologic response, differences in the attenuation of individual antibody levels, and the complexity added by the availability of different vaccines, dosing regimens, and decay rates, a better methodology for determining when a specific individual requires re-vaccination should be determined. With no current correlations of protection, especially in populations in which preventing infection is the goal, the higher the antibody titer the better. Studies have demonstrated that those who were vaccinated for SARS-CoV-2 are generally in favor for receiving additional booster doses. Furthermore, an increase in significant adverse events, other than lymphadenopathy, have not been reported in recipients of additional SARS-CoV-2 vaccine doses beyond the primary series.^{vii} The effectiveness of additional booster vaccination over the primary vaccination series in preventing re-infection with SARS-CoV-2 for currently available vaccine types have been demonstrated in a number of studies^{viii,ix}, only the timing of when and to whom to give booster dosing remains in debate. Lastly, multiple studies illustrate that the maximizing of timing between vaccination doses, regardless of mRNA or adenovirus vaccination type, results in improved immunologic responses both in initial degree, but also in the persistence of response.^{x,xi,xii,xiii}

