The design for this study is an observational cohort study utilizing prospectively collected electronic medical record (EMR) data from usual clinical care at AHF Midtown Manhattan Healthcare Center, obtained from the OPERA® Observational Database.

The study population will consist of adults vaccinated against SARS-CoV-2 virus receiving the Roche SARS-CoV-2 Semi-Quant Spike Ig AB test as part of their usual clinical care. These individuals will be followed from vaccination until study end.

EXPOSURES OF INTEREST

Initial vaccination with Pfizer, Moderna, and J&J COVID vaccines, booster vaccination with Pfizer, Moderna, and J&J vaccines, and concordant boosting versus discordant boosting

SUBGROUPS OF INTEREST

HIV-positive versus HIV-negative patients, individuals with at least 2 measurements of antibody levels, and boosted individuals are the subgroups of interest.

STUDY ENDPOINTS

Endpoints for both the primary and secondary objectives are non-responders and low responders and rates of decline of SARS-CoV-2 antibodies

- Non-response will be defined as: 0 to <50 U/mL
- Low response will be defined as: ≥ 51 to ≤ 250 U/mL
- Adequate response will be defined as: >251 U/mL

Roche's Elecsys semi-quantitative spike Ab Ig assay is a commercially available assay that can potentially be utilized to help guide the need for an additional vaccination dose based upon the levels of antibodies that have been previously clinically correlated with neutralizing antibodies. As part of routine care, Ab Ig assays were performed for some patients at the AHF Midtown Manhattan Healthcare Center and results were recorded in their EHR.

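### Objective 5 describes pre-infection titres in infected patients only, so it cannot show even the direction of any link between titre and breakthrough infection

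*Combined protocol and SAP*

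**What the plan says.** Section 3 lists Objective #5 as secondary: "Recording breakthrough infections after vaccinations and assessing antibody levels pre-breakthrough infection". Section 7 gives its method in two steps. The search is broad: "Among all individuals with full vaccination and antibody testing, the EHR will be searched for documentation of COVID infection after vaccinations". The output is narrow: "If breakthrough infections are observed, antibody levels prior to infection will be described". A note adds that infections diagnosed outside the clinic may be missing from the record.

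No other section plans a comparison of infection by titre:

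- Section 6, Study Endpoints: "Endpoints for both the primary and secondary objectives are non-responders and low responders and rates of decline of SARS-CoV-2 antibodies". Infection is not named.
- Section 7, Objective #1: the Poisson incidence rates are for response categories, not for infection.
- Section 7, Subgroup Analyses: these concern vaccine types, vaccine combinations and serial titres. Sensitivity analyses are marked as not applicable.

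The wider purpose goes further than Objective 5. The title asks whether titres should guide boosters, and the Synopsis includes the aim "to measure the efficacy of utilizing these antibody measurements to help guide the timing of booster doses". The Background says "With no current correlations of protection", and takes from cited outside studies that "post vaccination waning antibody levels are highly correlated with risk of re-infection, severe disease, and hospitalization".

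**The concern.** A set of titres from infected patients can be interpreted only against the titres of the people and follow-up time from which those infections arose. If most cases had low titres, that could mean low titre carries risk, or simply that most of the cohort had low titres. The plan collects what is needed to tell these apart, because the infection search covers every tested patient, but it uses only the infected part.

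At stake is how the cut-points are read. Objective 5 is the one place where the study's own data could set titre against infection. A case-only listing, published under a title about titre-guided boosting, invites readers to see support for the 50 and 250 cut-points, or evidence against them, that the output cannot provide. Section 7 also does not say which prior titre is described: the first, the last, or one before or after a booster.

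**Working it through.** The documents give no sample size, event count, effect size or power for Objective 5, so there is no stated figure to reproduce. Apart from the clinic size in step 4, all inputs below are assumptions chosen to show a range.

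1. **Formula.** Let c be the share of infections whose last titre was at or below 250, and s the share of cohort person-time at or below 250. With E infections and T person-time in total, the rate at low titre is cE/(sT) and the rate at adequate titre is (1−c)E/((1−s)T). E and T cancel, so the rate ratio is (c/s) / ((1−c)/(1−s)). Objective 5 estimates c and says nothing about s.

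2. **One case-only result, three conclusions.** Take c = 0.30.
   - s = 0.15: (0.30/0.15)/(0.70/0.85) = 2.43
   - s = 0.30: (0.30/0.30)/(0.70/0.70) = 1.00
   - s = 0.50: (0.30/0.50)/(0.70/0.50) = 0.43

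3. **Other values of c.**

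| Share of cases low (c) | s = 0.10 | s = 0.20 | s = 0.40 | s = 0.60 |
|---|---|---|---|---|
| 0.20 | 2.25 | 1.00 | 0.37 | 0.17 |
| 0.40 | 6.00 | 2.67 | 1.00 | 0.44 |
| 0.60 | 13.5 | 6.00 | 2.25 | 1.00 |

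The ratio equals 1 whenever s = c and falls on either side of 1 otherwise. Without s, even the direction is not determined.

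4. **Precision of a comparison, if added.** Section 4 gives 993 + 946 = 1,939 patients in care. This is a ceiling, since eligibility requires full vaccination and a later test. By Schoenfeld's formula, with two-sided alpha 0.05 and 80% power, events needed = (1.960 + 0.842)² / (a(1−a)(ln HR)²), where a is the low-titre share.
   - HR 2, a = 0.10: 7.849/(0.09 × 0.4805) = 181.5, so 182 infections (182/1,939 = 9.4%).
   - HR 2, a = 0.40: 7.849/(0.24 × 0.4805) = 68.1, so 69 infections (69/1,939 = 3.6%).
   - With 20 infections, power for HR 2 is 15% to 33% over a = 0.10 to 0.40. With 100 infections it is 55% to 92%.

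The comparison may therefore be imprecise, which argues for an exploratory label.

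**The case against.** The strongest reply is that the plan does what Objective 5 says. The objective is to record infections and assess prior titres, and Section 7 does that. A reader might infer that the plan fails its own objective. The documents do not support this: Objective 5 promises no risk comparison, and infection is not a listed endpoint. The gap is between Objective 5 and the study's title and aim.

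Three other inferences also go too far.

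- A reader might take the Synopsis to claim that testing identifies people at high risk. The phrase "the potential usage of quantitative antibody testing to determine those at greatest risk for infection" stands in a sentence listing topics on which few data exist, so it names an evidence gap. The aim about guiding booster timing is the firmer anchor.
- A reader might infer that infection is the study's only clinical outcome. Objective #3 also describes side effects after boosters. Infection is the only outcome that bears on protection.
- A reader might infer that no denominator of any kind will be reported. Objective 1 gives the frequency of each response level in the tested cohort, which would probably differ between the scenarios above. Only the Objective 5 output would be the same in all of them. Objective 1 does not close the gap, however, because its distribution is not linked to infection, follow-up time or boosting.

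A further objection stands in part: a comparison would itself be confounded. Section 6 says that non-responders and low responders were offered boosters because of their titre, and that only some patients were tested. These points limit what a comparison can show. They do not favour the case listing, which has the same selection and under-capture and no denominator.

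**Conclusion.** The point holds as a gap between a descriptive secondary analysis and the study's stated aim. Titres in cases alone leave the direction of any titre-infection association undetermined. That conclusion follows from the formula and does not depend on the assumed shares. The specific ratios are illustrations: they show that opposite conclusions fit the same listing, and they do not estimate a bias in this study. The primary objectives are unaffected. The change is worth making because the data are already held and the plan already uses Poisson regression with person-time, but its result would be exploratory and possibly imprecise.

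**What to change.** Keep the case listing and the under-capture note, and state which prior titre is listed. Then add one exploratory table to Objective 5:

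- **Content:** breakthrough infections, person-time, and rates with 95% confidence intervals by most recent titre category (non, low, adequate).
- **Person-time:** count from each qualifying test to the earliest of next test, booster, infection, last clinical contact or study end.
- **After a booster:** put time between the booster and the next titre in its own category. The Synopsis requires at least 3 weeks before a post-booster measurement and Section 7, Objective #3 at least 2 weeks. These need to be reconciled so that a qualifying post-booster test is defined.
- **Adjustment:** if events allow, include calendar time and a few covariates already collected, such as age and HIV status. Otherwise report counts and person-time only.
- **Statement of limits:** titre-triggered booster offers, testing of only some patients, waning since the last test, and missed outside diagnoses all restrict interpretation. Objective 5 cannot by itself validate the 50 and 250 cut-points.

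The cost is some programming to build a time-updated dataset with infection dates and censoring rules, and wide intervals if infections are few. No new data collection is needed.
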